4.2.2. Exclusion criteria

Patients meeting any of the following exclusion criteria are not to be enrolled in the study:

1. Female patients who are lactating or have a positive serum pregnancy test during the screening period.
2. Major surgery within 28 days before enrollment.
3. Radiotherapy within 14 days before enrollment, but if the involved field is small, 7 days will be considered a sufficient interval before onset of the treatment.
4. Glucocorticoid therapy within the 14 days prior to inclusion that exceeds a cumulative dose of 160 mg dexamethasone or 1000 mg prednisone.
5. Central nervous system involvement.
6. Infection requiring systemic antibiotic therapy or other serious infection within 14 days before study enrollment.
7. Active congestive heart failure (NYHA III-IV) (Appendix 3), symptomatic ischemia, conduction abnormalities uncontrolled by conventional intervention, acute diffuse infiltrative pulmonary disease, pericardial disease or myocardial infarction within 6 months prior to enrollment or left ventricular ejection fraction (LVEF) <40% within one month before randomization.
8. Ongoing or active systemic infection, active hepatitis A, B or C virus infection, or known human immunodeficiency virus (HIV) positivity.
9. Any other serious medical or psychiatric illness that could, in the investigator's opinion, potentially interfere with the completion of treatment according to this protocol.

Helsinki University Hospital Comprehensive Cancer Center Hematology
Clinical study protocol NMSG#24/15

10. Known allergy to Captisol (a cyclodextrin derivative used to solubilize carfilzomib) or to any of the study medications, their analogues, or excipients in the various formulations of any agent.
11. Contraindication to dexamethasone or any of the required concomitant drugs or supportive treatments, including hypersensitivity to antiviral drugs, or intolerance to hydration due to pre-existing pulmonary or cardiac impairment.
12. Diagnosed or treated for another malignancy within 5 years before study enrollment or previously diagnosed with another malignancy and have any evidence of residual disease. Patients with nonmelanoma skin cancer or carcinoma in situ of any type are not excluded if they have undergone complete resection.
13. Patient has \geq Grade 3 peripheral neuropathy, or Grade 2 with pain on clinical examination within the 14 days prior to inclusion.
14. Participation in another interventional study within the 28 days before this study inclusion.
15. Patients refractory to carfilzomib or elotuzumab.
16. Primary plasma cell leukemia, systemic AL amyloidosis, Waldenström macroglobulinemia, rare IgM multiple myeloma, POEMS syndrome, myelodysplasia
17. Allogeneic or autologous stem cell transplantation planned
18. Participants receiving any other investigational agents or received within 60 days
19. Pleural effusions requiring thoracocentesis within the 14 days prior the inclusion.
20. Ascites requiring ascitespunction within the 14 days prior to inclusion.
21. Previous allogeneic transplantation
22. Uncontrolled hypertension or uncontrolled diabetes despite medication

- 23. Known hepatic cirrhosis
- 24. Severe autoimmune disease
- 25. Positive direct antiglobulin test (DAT), Coombs test

4.2.3 DISCONTINUATION OF SUBJECTS FROM TREATMENT

Patients will be informed that they have the right to withdraw from the study at any time for any reason, without prejudice to their medical care. The investigator has also the right to withdraw patient from the study for any of the following reason.

Adverse event

Protocol violation

Lost to follow-up

Progressive treatment

Study termination

If the responsible physician thinks a change of therapy would be best for the patient

No compliance of the patient

Pregnancy

Death

Patients who are withdrawn will not be replaced. At the time of withdrawal, all study procedures outlines for the end of visit should be completed (Table 1. End of study). The primary reason for patient's withdrawal from the study is recorded in the source documents and CRF. If withdraw by investigator or patient will occur, the patient undergoes an end of study assessment, in which present disease stage and reason for end of study should be noted and be given appropriate care under medical supervision until symptoms cease or the condition becomes stable.

4.2.4 DISCONTINUATION IN CASE OF INTOLERABILITY

Helsinki University Hospital Comprehensive Cancer Center Hematology
Clinical study protocol NMSG#24/15

Patients will continue study treatment with dose reduction by the protocol in case of intolerability by the investigator decision. Study patient can continue study treatment with 1-2 drug combination if one of the study drugs has to be permanently discontinued.

5. TREATMENT

5.1 TABLE 6. STUDY DRUG ADMINISTRATION SCHEDULE

28-day cycle, carfilzomib will be infused first

Cycles 1-2			
Agent	Dose/day	Route	Days
Carfilzomib patients 1-5	20 mg/m ²	IV	1 (cycle 1)
	56 mg/m ²	IV	8, 15 (cycle 1)
patients 1-5	56 mg/m ²	IV	1, 8, 15 (cycle 2)
Elotuzumab	10 mg/kg	IV	1, 8, 15
Dexamethasone	40 mg	Oral/IV	1, 8, 15, 22

Cycles 1-2			
Agent	Dose/day	Route	Days
Carfilzomib -patients 6-40	20 mg/m ²	IV	1 (cycle 1)
	70 mg/m ²	IV	8, 15 (cycle 1)
	70 mg/m ²	IV	1, 8, 15 (cycle 2)
Elotuzumab	10 mg/kg	IV	1, 8, 15
Dexamethasone	40 mg	Oral/IV	1, 8, 15, 22

Cycles 3-8			
Agent	Dose/day	Route	Days
Carfilzomib - patients 1-40	70 mg/m ²	IV	1, 8, 15
Elotuzumab	10 mg/kg	IV	1,15
Dexamethasone	40 mg	Oral/IV	1, 8, 15, 22

Cycles 9 – until relapse or progression			
Agent	Dose/day	Route	Days
Carfilzomib - patients 1-40	70 mg/m ²	IV	1, 15
Elotuzumab	10 mg/kg	IV	1,15
Dexamethasone	40 mg	Oral/IV	1,15

5.2 CARFILZOMIB ADMINISTRATION

Patients will receive iv prehydration prior to each carfilzomib infusion during cycle 1. Prehydration will consist of 250 to 500 ml normal saline or other appropriate iv fluid.

Thereafter, carfilzomib prehydration should only be administered if the patients condition and/or risk factors require hydration. The total amount of prehydration will be reported and the reason for hydration after cycle 1 will be reported. Carfilzomib will be administered as an iv infusion over 30 minutes.

Carfilzomib for injection is supplied as a lyophilized parenteral product in single-use vials packaged in multi-vial cartons. Institutional pharmacies will be supplied with vials with adequate study labeling. Study treatments should be stored in a securely locked area with access limited to appropriate study personnel. Carfilzomib must be stored at 2°C to 8°C in a refrigerator. Carfilzomib vials must be kept in cartons in order to protect from light until ready for reconstitution. One carfilzomib is reconstituted and inspected, the clear solution may be stored in a refrigerator (recommended) controlled temperature from 2°C to 8°C for up to 24 hours. Once reconstituted, carfilzomib must be used within 4 hours if not refrigerated and within 24 hours if it has been stored in a light-tight refrigerator. The lyophilized product is reconstituted with sterile water for injection, to a final carfilzomib concentration of 2.0 mg/ml prior to administration. The dose will be calculated using the patient's actual body surface area (BSA) at baseline. Patients with a BSA > 2.2 m² will receive a dose based upon a 2.2 m² BSA. Dose adjustments must be made for weight gains/losses of ≥ 20% of baseline body weight.

Mechanical infusion pumps are recommended but gravity-dependent infusions are permitted if the 30-minute infusion duration can be reliably maintained.

Helsinki University Hospital Comprehensive Cancer Center Hematology
Clinical study protocol NMSG#24/15

Carfilzomib infusion must occur at a facility capable of managing hypersensitivity reactions. Patients will be hospitalized overnight after first infusion of the study drug combination. Patients will remain at the investigational site under observation for at least one hour following each infusion of carfilzomib in cycle 1. Carfilzomib must be administered via a dedicated iv line. If a permanent infusion device (e.g. Porta-Cath) is used for infusion the line must be flushed with a minimum of 20 ml of normal saline prior to and following carfilzomib infusion.

5.2.1 DOSE MODIFICATION GUIDELINES FOR CARFILZOMIB

In a case of study related adverse event the clinical investigator must assess its possible relationship to carfilzomib in addition to elotuzumab and dexamethasone.

Table 7. Carfilzomib dose reduction guidelines for toxicity and dose modification			
	1 st dose reduction	2 nd dose reduction	3 rd dose reduction
70 mg/m ²	56 mg/m ²	45 mg/m ²	36 mg/m ²

The basic principle is that if a patient requires an interruption of carfilzomib of more than four weeks this study patient will be removed from study; all exceptions to this must be discussed with principal investigator. If the carfilzomib dose is reduced once, it will be continued for at least one cycle. In case of excellent toleration of this cycle, the dose level prior to reduction may be resumed by the investigator's discretion.

Table 8.

Carfilzomib dosing guidelines for treatment- emergent hematologic toxicity

Hematologic toxicity	Recommended action
Thrombocytopenia	
If platelets $\leq 30 \times 10^9/l$	If $10-30 \times 10^9/l$ without bleeding continue the same dose If evidence of bleeding or platelets $< 10 \times 10^9/l$, withhold dose until platelets return to $\geq 10 \times 10^9/l$ and/or bleeding is controlled, then resume the same dose
For each subsequent drop to $\leq 30 \times 10^9/l$	If $10-30 \times 10^9/l$ without bleeding continue at the same dose If evidence of bleeding or platelets $< 10 \times 10^9/l$, withhold dose until platelets return to $\geq 10 \times 10^9/l$ and/or bleeding is controlled, then resume at 1 dose reduction.
Neutropenia	
If ANC $\leq 0.75 \times 10^9/l$	If ANC $0.5-0.75 \times 10^9/l$, continue at the same dose If ANC $< 0.5 \times 10^9/l$, withhold dose until ANC returns to $\geq 0.5 \times 10^9/l$, then resume at the same dose.
For each subsequent drop to $\leq 0.75 \times 10^9/l$	If ANC $0.5-0.75 \times 10^9/l$, continue at the same dose If ANC $< 0.5 \times 10^9/l$, withhold dose until ANC returns to $\geq 0.5 \times 10^9/l$, then resume at 1 dose reduction
Neutropenic fever	If ANC $< 0.5 \times 10^9/l$, and single temperature $> 38.5^\circ\text{C}$ or temperature $> 38.0^\circ\text{C}$ more than one hour, withhold dose until ANC returns to baseline level, then resume at the same dose.

ANC = absolute neutrophil count.

Helsinki University Hospital Comprehensive Cancer Center Hematology
Clinical study protocol NMSG#24/15

Conditions not requiring dose reduction of carfilzomib

- Grade 3 nausea, vomiting or diarrhea, unless persisting more than 3 days with adequate treatment of antiemetics or antidiarrheal agents
- Grade 3 dexamethasone-related hyperglycemia
- Grade 3 fatigue, unless persisting for > 14 days
- Alopecia

Table 9. Carfilzomib dosing guidelines for nonhematologic toxicity

Nonhematological toxicity	Recommended action
Renal dysfunction	
Serum creatinine equal to or greater than 2 x baseline, or CrCl < 15 ml/min, or decreases to ≤ 50% of baseline or need for dialysis	Withhold dose and continue monitoring the renal function If attributable to carfilzomib, resume when renal function has recovered to within 25% of baseline, start at 1 dose level reduction If not attributable to carfilzomib, dosing may be resumed at the discretion of the physician Patient will be withdrawn from study in case of permanent dialysis need
≥ grade 3 elevation in liver function tests	Withhold dose and resume at 1 dose reduction level when toxicity has recovered to baseline
Grade 3 infection	Withhold carfilzomib until infection resolves and resume at the same dose
Congestive heart disease	Any subject with symptoms of congestive heart failure, whether or not drug related, must have the dose held until return to baseline, after which treatment may continue at a reduced dose, or consider discontinuation of study protocol. If no recovery in 4 weeks, patient must be withdraw.
Left ventricular ejection fraction	
For resting LVEF < 40% or reduction of LVEF to < 55% if the drop is greater than 20% form baseline	Withhold until LVEF returns to > 40% or, if held due to a drop to < 55%, to within 15% of baseline and resume at 1 dose reduction.
Other grade 1 or 2 nonhematologic toxicity	Continue at the same dose
Any other drug-related nonhematologic toxicity ≥ grade 3	If attributable to carfilzomib, withhold dose Resume at 1 dose reduction when toxicity has resolved to grade 2 or less or to baseline If tolerated, the reduced dose may be escalated to the previous dose at the discretion of the physician
PRES: posterior reversible encephalopathy syndrome; headache, altered mental status,	Stop carfilzomib and study treatment and the patient is withdrawn from study. In visual or

Helsinki University Hospital Comprehensive Cancer Center Hematology
Clinical study protocol NMSG#24/15

seizures, visual loss, hypertension	neurological symptoms	neuroradiological imaging is recommended.
-------------------------------------	-----------------------	---

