ELO will be given on cycle days 1 and 15.

Dexamethasone as in cycles 1-2.

Cycles 9 -

CAR, ELO and Dex will be given on days 1 and 15 from cycle 9 until relapse or progression or excess toxicity.

Duration of Study:

Expected duration of treatment:

- patient recruitment 24 months
- primary endpoint (ORR) together with the relevant secondary endpoints will be assessed after the minimum follow-up of one year has been reached with the last included patient
- to assess PFS and TTNT all patients will be followed until 4 years after first dose

Helsinki University Hospital Comprehensive Cancer Center Hematology
Clinical study protocol NMSG#24/15

LIST OF ABBREVIATIONS AND GLOSSARY OF TERMS

Common abbreviations used in oncology protocols are provided below. Program-specific or protocol-specific abbreviations must be added to this list, and unnecessary abbreviations removed, as applicable. Abbreviations that are retained should not be changed.

Abbreviation	Term
AE	adverse event
AFOS	alkaline phosphatase
ALT, ALAT	alanine aminotransferase
ANC	absolute neutrophil count
API	active pharmaceutical ingredient
ASCO	American Society of Clinical Oncology
ASCT	Autologous stem cell transplantation
ASO-RQ	Allele specific oligonucleotide real-time quantification
AST	aspartate aminotransferase
AUC	area under the plasma concentration versus time curve
AUC _{24 hr}	area under the plasma concentration versus time curve from zero to 24 hours
AUC _{inf}	area under the plasma concentration versus time curve from zero to infinity
AUC _τ	area under the plasma concentration versus time curve from zero to next dose
BID	bis in die; twice a day
BM	bone marrow
BSA	body surface area
BUN	blood urea nitrogen
BZM	Bortezomib
CBC	complete blood count
CL	clearance, IV dosing
CL _p	plasma clearance
CL _{Total}	total clearance
C _{max}	single-dose maximum (peak) concentration
CNS	central nervous system
CR	complete remission
CrCl	Creatinine Clearance
CRO	Clinical trial research organization
CRP	C-reactive protein
CT	computed tomography

Helsinki University Hospital Comprehensive Cancer Center Hematology
Clinical study protocol NMSG#24/15

Abbreviation	Term
CY	Cyclophosphamide
CYP	cytochrome P ₄₅₀
DDI	drug-drug interaction
DLT	dose-limiting toxicity
DME	drug metabolizing enzymes
DNA	deoxyribonucleic acid
DSRT	Drug sensitivity and resistance testing
ECG	Electrocardiogram
ECOG	Eastern Cooperative Oncology Group
eCRF	electronic case report form
ELISA	enzyme-linked immunosorbent assay

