3. ETHICAL AND REGULATORY CONSIDERATIONS

The study will be conducted in accordance with the ethical principles of the Declaration of Helsinki, the ICH-GCP Guidelines, the EU Clinical Trial Directive (2001/20/EG), as may be amended or replaced, and applicable regulatory requirements. The local investigator is responsible for the proper conduct of the study at the study site. Approval of the study protocol and any substantial amendment will be requested from the National Ethics Committees of Finland and Sweden, the Finnish Medicines Agency and the Swedish Health Authority Medical Products Agency (MPA) by the Sponsor-Investigator. The Sponsor-Investigator will provide National Ethics Committees` and the Finnish Medicines Agency's and Medical Products Agency`s above mentioned approvals to Bristol-Myers Squibb and Amgen.

In accordance with the Declaration of Helsinki patients have the right to withdraw from the protocol at any time for any reason. The investigator also has the right to withdraw patients from the protocol in the event of intercurrent illness, adverse events and treatment failure after a prescribed procedure, protocol violations, cure, administrative reasons or other reasons. If a patient decides to withdraw from the protocol, all efforts will be made to complete and report the observations as thoroughly as possible. A complete final evaluation at the time of the patient's withdrawal should be made together with the reason.

The clinical trial investigator-sponsor is the physical person or legal entity which is interested in the performance of the trial, signs requests for authorization addressed to the National Ethics Committee (EC) and regulatory authority of Finland and is responsible for the trial, including its performance, initiation and completion. The investigator-sponsor will be responsible for ensuring compliance with applicable legal guidelines. Investigators must agree with this protocol and

Helsinki University Hospital Comprehensive Cancer Center Hematology
Clinical study protocol NMSG#24/15

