3.3. STUDY INSURANCE

Before the start of the study the sponsor-investigator and principal investigator of each site will ensure that adequate insurance for patients is in place covering losses due to death or injury resulting from the study, in accordance with applicable laws and regulations in each country where the trial is conducted (Finland, Sweden). Adequate insurance for investigators and study staff will be ensured. The pharmaceutical company supplying drugs used in the study must have their own liability insurance.

4. INVESTIGATIONAL PLAN Study design and duration

This is an investigator initiated, academic, non-randomized, open-label multicenter phase 2 study for patients with multiple myeloma in relapse or progression after 1 to 3 prior treatment lines and in need of therapy.

All patients will receive successive cycles of CAR + ELO + Dex according to the schedule shown in Table 2 and 6. Cycles are to be continued until progression, relapse or excess toxicity. The primary objective is to assess the overall response rate obtained with the regimen. This study will have phase 2a portion with 40 included patients to show the feasibility and safety of this design and if observed will be expanded to phase 2b portion with additional number of patients based on statistical power calculations..

4.1 Study procedures:

At registration each patient will have an unique identification number and following details will be documented:

- Name of study center and responsible investigator
- Date of birth of study patient
- Date of signed informed consent

Helsinki University Hospital Comprehensive Cancer Center Hematology
Clinical study protocol NMSG#24/15

- Date of treatment start

The study patient is considered enrolled on first day of study protocol treatment. Any study related investigations are not started before written informed consent.

- At inclusion: before the start of protocol treatment blood- and urine values within 2 weeks before study start, bone marrow samples within 4 weeks and bone imaging within 2 months
- During treatment: within 5 days before next cycle
- At progression and if patient is taken/withdrawn off protocol

All patients will be followed until 3 years after onset of the treatment protocol.

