5.4.3 PROHIBITED AND/OR RESTRICTED TREATMENTS

Other antimyeloma treatment than study protocol treatment during the study is not allowed. Glucocorticoids are allowed to use for nonmalignant situation like asthma with a dose of no more than ≤ 4 mg/day dexamethasone or prednisone ≤ 20 mg/day. Need of plasmapheresis indicates myeloma progression and the patient will end the study treatment.

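### Minor: Section 5.2.1 removes a patient off carfilzomib for more than four weeks from the study, where removal from study treatment with continued PFS/TTNT follow-up is the likely intent, and it is not linked to Section 4.2.4

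*Protocol*

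**What the plan says.** **Long carfilzomib interruption.** Section 5.2.1 sets out a basic principle for interrupted dosing: "carfilzomib of more than four weeks this study patient will be removed from study; all exceptions to this must be discussed with principal investigator".

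**Permanent stop of one drug.** Section 4.2.4, on intolerability, says: "Study patient can continue study treatment with 1-2 drug combination if one of the study drugs has to be permanently discontinued". It does not except carfilzomib. Sections 4.2.4 and 5.2.1 do not refer to each other.

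**What happens at withdrawal.** Under Section 4.2.3, "the patient undergoes an end of study assessment, in which present disease stage and reason for end of study should be noted". Section 3 adds: "A complete final evaluation at the time of the patient's withdrawal should be made together with the reason". Section 4.2.3 also provides for medical care until the patient is stable, and says that withdrawn patients are not replaced. Table 1 has no column after End of study.

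**Follow-up.** The synopsis (Duration of Study) says: "to assess PFS and TTNT all patients will be followed until 4 years after first dose". Section 4.1 says: "All patients will be followed until 3 years after onset of the treatment protocol".

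**Other wording for stopping.** Section 5.4.3 says: "Need of plasmapheresis indicates myeloma progression and the patient will end the study treatment". The PRES row of Table 9 says: "Stop carfilzomib and study treatment and the patient is withdrawn from study".

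**The concern.** PFS and TTNT are secondary endpoints that Section 9.2 estimates by Kaplan-Meier in everyone who received at least one dose. TTNT in particular normally occurs after study treatment has ended, so follow-up has to outlast treatment. If a site takes 5.2.1 at its word, it completes the end of study visit and stops collecting progression and next-treatment dates. The patient is then censored at a point set by toxicity, which may be related to prognosis. A statistical analysis plan can set a censoring rule, but it cannot recover dates that nobody collected.

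The second strand concerns treatment. A permanent carfilzomib stop necessarily exceeds four weeks, so it falls under both 5.2.1 (removal by default) and 4.2.4 (remaining drugs permitted). One site may continue elotuzumab and dexamethasone under 4.2.4 without asking, and another may take a similar patient off everything.

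**Working it through.** The protocol gives no figure on this point. Its one design figure, the 95% interval of 53-83% for an ORR of 70% with N = 40 (Section 9), reproduces as the exact interval for 28/40 (53.5% to 83.4%), but does not bear on the matter.

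**Step 1: the texts side by side.**

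| Question | Default in 5.2.1 | Elsewhere |
|---|---|---|
| Off carfilzomib more than 4 weeks: what ends? | The study | 5.4.3 ends study treatment in another setting |
| Endpoint follow-up afterwards? | Not mentioned | 4.2.3, Section 3 and Table 1: none described. Synopsis: all patients, 4 years. Section 4.1: all patients, 3 years |
| Remaining drugs after a permanent stop? | Only by exception, discussed with the principal investigator | 4.2.4: permitted, exception route not mentioned |

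No section separates leaving treatment from leaving follow-up.

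**Step 2: events lost per patient removed (illustration).** Assumptions: exponential PFS, S(t) = 2^(-t/m), with m = 18.7 months (carfilzomib-dexamethasone, Table 3). Removal at month r while progression-free; follow-up horizon H = 36 or 48 months. The earliest r shown is a carfilzomib stop at the start of cycle 3 plus four weeks: 2 × 28 + 28 = 84 days = 2.76 months.

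Expected events in 40 patients = 40 × (1 − 2^(−H/m)):
- H = 36: 29.5
- H = 48: 33.2

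Expected event lost per patient removed = 1 − 2^(−(H−r)/m):

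| r (months) | H = 36 | H = 48 |
|---|---|---|
| 2.76 | 0.708 | 0.813 |
| 6 | 0.671 | 0.789 |
| 12 | 0.589 | 0.737 |

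The extremes over other medians quoted in the protocol are 0.469 (m = 26.3, H = 36, r = 12) and 0.961 (m = 9.7, H = 48, r = 2.76). If 1 of 40 patients were removed, 1.9% to 2.5% of expected events would be lost over all scenarios; if 4 were removed, 7.6% to 9.9%. The counts 1 and 4 are assumptions.

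**Step 3: effect on the Kaplan-Meier median (illustration).** Simulation of 200,000 patients with m = 18.7, a 48-month horizon, a share of patients due for removal at a time uniform on 1 to 12 months, and the hazard after removal multiplied by k. Each cell gives the median with full follow-up, then the median with censoring at removal.

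| Share due for removal | k = 1 | k = 1.5 | k = 2 | Removed event-free, of 40 |
|---|---|---|---|---|
| 10% | 18.7 / 18.7 | 18.3 / 18.8 | 17.8 / 18.7 | about 3 |
| 20% | 18.6 / 18.6 | 17.7 / 18.7 | 17.0 / 18.7 | about 6 |
| 30% | 18.7 / 18.7 | 17.3 / 18.7 | 16.2 / 18.7 | about 9 |

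The overstatement is 0 months when the hazard is unchanged and 18.7 − 16.2 = 2.5 months at the far corner.

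**Step 4: exposure, only if no exception is granted.** For a permanent carfilzomib stop at the start of cycle 3 with removal four weeks later, the doses forgone in cycles 4-8 (Table 6) are at most 5 × 2 = 10 elotuzumab infusions and 5 × 4 = 20 dexamethasone doses (20 × 40 mg = 800 mg).

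**The case against.** The strongest reply is that the protocol uses the word study loosely for study treatment. Section 4.2.3 is headed as discontinuation from treatment. Table 1 labels its cycle columns as running until end of study. Section 4.1 lists assessment at withdrawal off protocol just before stating that all patients are followed. If the end of study assessment closed observation, TTNT would also be lost in patients who stop for progression, which cannot be intended. The PRES row is weak evidence of a deliberate two-term system, because it names carfilzomib and study treatment side by side although one includes the other. All of this stands as evidence of intent.

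A reader might infer that the protocol orders follow-up to stop, or that 5.2.1 and 4.2.4 flatly contradict each other. The documents support neither. No section says that follow-up ends for a removed patient. Section 5.2.1 is a principle with an express exception route, Section 7 also sends exceptional issues to the principal investigator, and 4.2.4 can be read as the specific rule. A reader might also take the loss of 2% to 10% of events as a forecast. It only rescales an assumed 1 to 4 removals, and lost events are not in themselves bias.

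What the reply does not remove is the ambiguity for a site. The statements that all patients are followed do not say that they cover patients removed under 5.2.1. The request in Section 3 for every effort to complete observations concerns patients who decide to withdraw, whereas removal under 5.2.1 is not the patient's decision.

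**Conclusion.** A minor but genuine wording fault. Taken literally, 5.2.1 ends PFS and TTNT observation at a toxicity-driven point for patients whom the synopsis and Section 4.1 mean to follow. For a permanent carfilzomib stop, the link between 4.2.4 and the exception route is left for sites to work out.

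Harm arises only if a patient is off carfilzomib for more than four weeks, no exception is granted, and the site reads the rule literally despite the general follow-up statements. The protocol gives no basis for the probability of any of these. The event losses rest on exponential PFS and medians borrowed from other regimens. The 2.5-month figure also needs 30% of patients due for removal and a doubled hazard, and it falls to zero if prognosis is unchanged. ORR, its interval and the sample size statement are not called into question. Censoring rules may sit in a statistical analysis plan that is not available, so their absence is not counted here.

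**What to change.** 1. In 5.2.1 and for the Table 9 withdrawals, write: *withdrawn from study treatment; follow-up for progression and next treatment continues until 4 years after first dose*.
2. Change the 3 years in Section 4.1 to the synopsis's 4 years, so that the new sentence points to a single horizon.
3. Cross-reference 4.2.4 and 5.2.1: *after a permanent carfilzomib stop the remaining drugs may continue under 4.2.4 after discussion with the principal investigator, except where Table 9 requires withdrawal*.

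The cost is a few sentences in an amendment, submitted as Section 8.2 requires. No patients or procedures are added, and follow-up does not go beyond what the synopsis already plans, although a site working to Section 4.1 would follow for one more year. The withdrawal reason is already recorded in the CRF under 4.2.3.

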4.2 STUDY POPULATION

4.2.1 Inclusion criteria

Each patient must meet all of the following inclusion criteria to be enrolled in the study:

1. Male or female patients at the age of 18 to below 75 years with the life expectancy of at least three months.
2. Prior confirmed diagnosis of multiple myeloma and measurable disease in blood or urine with at least one of the following: Serum M-protein $\geq 5\text{g/l}$, Urine M-protein $\geq 200\text{ mg/24 hours}$, In subjects without detectable serum or urine M-component, serum free light chain (S-FLC) $> 100\text{ ml/l}$ (involved light chain) and an abnormal serum kappa/lambda ratio
3. Relapse or progression after 1 to 3 prior treatment lines, which have included proteasome inhibitors (bortezomib, carfilzomib and/or ixazomib) and/or lenalidomide. Refractoriness to bortezomib, ixazomib and/or lenalidomide is allowed in the preceding cycle. Patients with previous autologous transplantation can be included.
4. Need of treatment of relapse or progression: IMWG criteria for relapse/progression (paraprotein or CRAB criteria or both). (Appendix 5)
5. Voluntary written consent must be given before performance of any study related procedure not part of standard medical care, with the

Helsinki University Hospital Comprehensive Cancer Center Hematology
Clinical study protocol NMSG#24/15

understanding that the patient may withdraw consent at any time without prejudice to future medical care.

6. Females of childbearing potential (FCBP) must have a confirmed negative serum pregnancy test within the 7 days prior to inclusion
7. Females of childbearing potential must use one effective method of contraception and their partners condom during the study and for 120 days following the last study drug treatment dose and male subjects who are sexually active with FCBP must agree to use condom during the study and for 180 days following the last study drug treatment dose.
8. Eastern Cooperative Oncology Group (ECOG) performance status 0-2, or Karnofsky at least 60. (Appendix 1)
9. Patients must meet the following adequate organ and bone marrow function within 21 days prior to inclusion:
 - Absolute neutrophil count (ANC) $1,000/\text{mm}^3$ ($\geq 1.0 \times 10^9/\text{L}$) and platelet count $75 \times 10^9/\text{L}$. Platelet transfusions to help patients meet eligibility criteria are not allowed within 3 days before study enrollment. Granulocyte growth factors are allowed to meet the inclusion criteria.

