7. SAFETY ASSESSMENT

Study investigators must follow the study protocol treatment and follow the dose reduction and adjustment guidelines in every study patient. Exceptional issues should be discussed with principal investigator. Adverse event will be documented if observed, mentioned during open questioning, or when spontaneously reported.

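### Table 8 gives two incompatible carfilzomib instructions for a repeat neutrophil drop below 0.5 x 10^9/l with fever, and nothing says which one governs

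*Protocol*

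**What the plan says.** Section 5.2.1 of the protocol sets out carfilzomib dose changes for hematologic toxicity in Table 8. Three of its entries act on an ANC below 0.5 x 10^9/l:

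- First drop: "withhold dose until ANC returns to $\geq 0.5 \times 10^9/l$, then resume at the same dose".
- Each subsequent drop: "withhold dose until ANC returns to $\geq 0.5 \times 10^9/l$, then resume at 1 dose reduction".
- Neutropenic fever, meaning ANC below 0.5 x 10^9/l with one temperature above 38.5 °C, or above 38.0 °C for more than one hour: "withhold dose until ANC returns to baseline level, then resume at the same dose".

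The two neutropenia rows do not mention fever. The fever row does not mention whether the episode is a first or a later one. Table 7 gives the reduction steps from 70 mg/m² as 56, 45 and 36 mg/m².

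The action column of Table 8 is headed as a recommendation, but section 7 states: "Study investigators must follow the study protocol treatment and follow the dose reduction and adjustment guidelines in every study patient".

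**The concern.** The fever row describes a special case of the event already covered by the neutropenia rows. If the protocol does not say that the special case overrides the general one, or the reverse, a febrile patient falls under both. On a repeat drop the two instructions cannot both be followed.

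Sites could then treat the same event differently, both in how long carfilzomib is held and in the dose at which it resumes. Safety and feasibility are part of the primary objective (section 2.1), and section 10.1 says that there is no earlier experience with this combination. Dose intensity and toxicity data from 40 patients are easier to interpret if every site applies the same rule.

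**Working it through.** The documents give no figure to reproduce here. The check is a comparison of the rows by trigger, restart count and dose, followed by a search for a priority rule.

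**Step 1: do the triggers overlap?** The fever row needs ANC below 0.5 x 10^9/l plus fever. The neutropenia rows need ANC below 0.5 x 10^9/l and set no condition on temperature. So the fever trigger lies wholly inside the neutropenia trigger.

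**Step 2: what does each row instruct?**

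| Event (ANC below 0.5 x 10^9/l) | Neutropenia row | Fever row | Do they agree? |
|---|---|---|---|
| First drop, no fever | restart at 0.5 or above, same dose | does not apply | only one row applies |
| First drop, with fever | restart at 0.5 or above, same dose | restart at baseline, same dose | dose yes, restart count no |
| Subsequent drop, no fever | restart at 0.5 or above, one reduction | does not apply | only one row applies |
| Subsequent drop, with fever | restart at 0.5 or above, one reduction | restart at baseline, same dose | neither |

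The restart conflict therefore arises at every febrile episode. The dose conflict arises only when the febrile episode is a subsequent drop. Table 8 counts drops to 0.75 x 10^9/l or below, so a patient's first fever can already be a subsequent drop.

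**Step 3: how far apart are the instructions?**

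- Dose: for a patient on 70 mg/m², one step down in Table 7 is 56 mg/m². 70 / 56 = 1.25, so the unreduced dose is 25% higher.
- Restart count: inclusion criterion 9 (section 4.2.1) requires an entry ANC of at least 1.0 x 10^9/l. If baseline means the entry value, the ratio of restart counts is at least 1.0 / 0.5 = 2. Table 8 does not define baseline, so this is an assumption.

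**Step 4: does any other text set a priority?** None was found.

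- The list in section 5.2.1 of conditions that need no reduction does not include neutropenic fever.
- Table 9 has an entry for grade 3 infection: "Withhold carfilzomib until infection resolves and resume at the same dose". It may apply to the same patient, adds a further restart condition, and does not say how it ranks against Table 8.
- Section 7 refers exceptional issues to the principal investigator, but a repeat febrile drop is an event that the table itself covers, twice.

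**The case against.** The best defence is that a specific row governs its own event. Read that way, the fever row is a coherent rule, with a longer hold and an unchanged dose, and it resembles the grade 3 infection entry in Table 9. Much of this stands as an account of what may have been meant. It does not settle the matter, because the protocol does not state that reading, and the subsequent-drop row is worded to cover each such drop without exception.

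A reader might also infer several stronger things that the documents do not support:

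- *That the more serious event gets the milder treatment.* On a repeat drop this is true only of the dose level, and only if the fever row governs. The fever row's hold is the stricter one where baseline exceeds 0.5 x 10^9/l. Which combination is preferable is a clinical question on which this review takes no view.
- *That a febrile patient returns to full dose without limit.* The same dose means the current dose, which may already be reduced, and a later afebrile drop below 0.5 x 10^9/l would call for a reduction. In the other direction, section 5.2.1 lets a reduced dose return to the earlier level after a well-tolerated cycle.
- *That waiting for baseline forces patients out.* Section 5.2.1 does say that "if a patient requires an interruption of carfilzomib of more than four weeks this study patient will be removed from study", but as a basic principle whose exceptions are discussed with the principal investigator. The documents give no recovery times.
- *That baseline is inflated by growth factor.* Section 4.2.1 says "Granulocyte growth factors are allowed to meet the inclusion criteria", so a supported entry value is possible. No figure shows by how much, and section 5.4.2 also allows growth factors to treat neutropenia, so the recovery may be supported as well.

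The gap of 70 against 56 mg/m² is not universal either. Patients 1 to 5 receive 56 mg/m² for the rest of cycles 1 and 2 after the first 20 mg/m² dose.

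**Conclusion.** The contradiction holds. For a repeat ANC below 0.5 x 10^9/l with fever, Table 8 gives two restart counts and two doses, and a site that section 7 obliges to follow the guidelines cannot comply with both. For a patient on 70 mg/m² the difference is one Table 7 level, 56 against 70. For a first drop with fever only the restart count is in conflict, by a factor of at least two if baseline is the entry value.

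Its reach is limited. The documents give no frequency for repeat febrile neutropenia, so the number affected is unknown and probably small. The sample size and the stated 53-83% interval for the response rate do not depend on it. It is a matter of consistent dosing and clean safety data, worth correcting because the rule is binding. The finding is that the rows disagree, not that either of them is the wrong clinical rule.

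**What to change.** Amend Table 8 so that the neutropenia and neutropenic-fever rows are reconciled:

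- State which row governs when a patient meets both.
- State whether the fever row covers repeat episodes or only the first.
- Define the baseline level: which measurement, taken when.
- While the table is open, say how the grade 3 infection entry in Table 9 relates to these rows.

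The dose and the restart count are for the sponsor to choose. The cost is a short table amendment, submitted under section 8.2 like any other, with a notice to sites. It needs no new data collection and no change to the sample size or the planned analyses.
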